8.4.4.4 Infection

The immune system effects of fingolimod may increase the risk of infections, including opportunistic infections. Before initiating study treatment, a complete blood count (CBC) will be collected and active infections are excluded. During the study treatment, a complete blood count will be collected regularly. Participants receiving fingolimod should report any signs or symptoms of infection to their investigator during therapy. Because elimination of fingolimod after discontinuation of fingolimod may take up to two months, vigilance for infection should be continued throughout this period. However, co-administration of a short course of corticosteroids treatment for relapse did not increase the overall rate of infection in participants treated with fingolimod in the Phase III clinical trials, compared to placebo.

8.4.5 Appropriateness of safety measurements

Beside routine safety assessments (physical and neurological examination, vital signs and laboratory assessments) few specific additional safety assessments are recommended in this study which are expected and known based on the mechanism of action of fingolimod and previous clinical data.

Effects of fingolimod on heart rate and conduction are expected and known based on mechanism of action and previous clinical data. Although clinically symptomatic cardiac events or clinically relevant ECG abnormalities have been reported at very low frequencies in the clinical development program especially with fingolimod 0.5mg/day dose treatment initiation of fingolimod will be monitored over 6 hours at the investigational site in this study.

Ophthalmologic examinations will be conducted in this study based on its previous use in the evaluation of retinal thickness and the detection of macular edema. Macular edema is an adverse event of special interest in participants treated with fingolimod because of the higher incidence seen in treated participants compared to active and placebo control groups, particularly when higher doses were evaluated in the clinical development program. The majority of cases of macular edema observed in participants treated with fingolimod occurred within the first three to four months after initiation of treatment. Therefore, an OCT scan is foreseen to be completed at Screening and Month 3.

Annual complete skin examinations have also been included to support regular monitoring of participants for the potential development of new skin cancers during the study.

Minor dose-dependent reductions in FEV1 and DLCO values were observed with fingolimod treatment starting at month 1 and remaining stable thereafter. And the reduction of FEV1 and DLCO from baseline value is resolved after treatment discontinuation. So pulmonary function tests will be conducted in all the participants at the screening and can be performed when participants with any reported AE related to respiratory disease, as per the investigator's discretion.

8.5 Additional assessments

8.5.1 Clinical Outcome Assessments (COAs)

The impact of multiple sclerosis on neurologic impairment will be assessed by Expanded Disability Status Scale (EDSS).

The objectives of EDSS are to confirm relapse

[REDACTED], it can be used in all the MS participants. The EDSS is an ordinal scale used for assessing neurologic impairment in MS based on a neurological examination. The scale consists of seven functional systems (FSs) and an ambulation score that are then combined to determine the EDSS steps. The FSs are Visual, Brain Stem, Pyramidal, Cerebellar, Sensory, Bowel & Bladder, and Cerebral functions. EDSS steps (ranging from 0(normal) to 10(death due to MS)), the higher score means the worsening of neurological status. The FSs and EDSS steps will be assessed in a standardized manner.

EDSS assessments are scheduled at screening visit, [REDACTED] [REDACTED] In the case of MS relapse, EDSS assessment is required at every unscheduled visit to confirm relapse.

A large black rectangular redaction box covers the majority of the page content, from approximately y=113 to y=885. The redaction is irregular, with a jagged bottom edge and several small white rectangular openings along the right and bottom edges, suggesting a redacted document page.

9 Study discontinuation and completion

9.1 Discontinuation

9.1.1 Discontinuation from study treatment and from study

Discontinuation of study treatment for a participant occurs when study treatment is permanently stopped for any reason (prior to the planned completion of the study drug administration, if any) and can be initiated by either the participant or the investigator.

The investigator must discontinue study treatment for a given participant if, he/she believes that continuation would negatively impact the participant's well-being.

Discontinuation from study treatment is required under the following circumstances:

- Participant/guardian decision
- Pregnancy

- Use of prohibited treatment as per recommendations in the prohibited treatment section
- Any situation in which continued study participation might result in a safety risk to the participant

Take into consideration the following to establish the list of circumstances under which study treatment must be discontinued:

- Adverse events, abnormal laboratory values or abnormal test result that indicate a safety risk to the participant. Refer to [Section 16.7](#) for Guidance for safety monitoring
- Unsatisfactory therapeutic effect
- Participant's condition no longer requires study treatment

If discontinuation from study treatment occurs, the investigator should make a reasonable effort to understand the primary reason for the participant's discontinuation from study treatment and record this information.

Participants who discontinue from study treatment should be asked to agree to **return for the end of treatment (EOT) and follow up visits indicated** in the Assessment Schedule [Table 8-1](#) (refer to section 8).

If the participant cannot or is unwilling to attend any visit(s), the site staff should maintain regular telephone contact with the participant, or with a person pre-designated by the participant. This telephone contact should preferably be done according to the study visit schedule.

After discontinuation from study treatment, at a minimum, in abbreviated visits, the following data should be collected at clinic visits or via telephone/email contact:

- New / concomitant treatments
- Adverse Events / Serious Adverse Events

9.1.2 Discontinuation from study

Discontinuation from study is when the participant permanently stops receiving the study treatment, and further protocol-required assessments or follow-up, for any reason. If the participant agrees, a final evaluation at the time of the participant's study discontinuation should be made as detailed in the assessment table (refer to Section 8).

9.1.3 Lost to follow-up

For participants whose status is unclear because they fail to appear for study visits or fail to respond to any site attempts to contact them without stating an intention to discontinue from study treatment or discontinue from study or withdraw consent/ exercise data privacy rights, the investigator must show "due diligence" by documenting in the source documents steps taken to contact the participant, e.g. dates of telephone calls, registered letters, etc. A participant should not be considered as lost to follow-up until due diligence has been completed or until the end of the study.

9.2 Withdrawal of informed consent/opposition to use data/biological samples

Participants may voluntarily withdraw consent to participate in the study for any reason at any time. Withdrawal of consent/ exercise the use of their data/privacy rights occurs in countries where the legal justification to collect and process the data is consent and only when a participant:

- Explicitly requests to stop use of their data and
- No longer wishes to receive study treatment
- Does not want any further visits or assessments (including further study-related contacts)

This request should be per local regulations (e.g. in writing) and recorded in the source documentation.

Withdrawal of consent impacts ability to further contact the participant, collect follow-up data (e.g. to respond to data queries) and potentially other country-specific restrictions. It is therefore very important to ensure accurate recording of withdrawal vs. discontinuation based on the protocol definitions of these terms.

In this situation, the Investigator should make a reasonable effort (e.g. telephone, e-mail, letter) to understand the primary reason for the participant's decision to withdraw their consent/exercise data privacy rights and record this information. The Investigator shall clearly document if the participant has withdrawn his/her consent for the use of data in addition to a study discontinuation.

Study treatment must be discontinued and no further assessments conducted, and the data that would have been collected at subsequent visits will be considered missing.

Further attempts to contact the participant are not allowed unless safety findings require communicating or follow-up.

All efforts should be made to complete the assessments prior to study withdrawal. If the participant agrees, a final evaluation at the time of the participant's study withdrawal of consent/exercise data privacy rights should be made as detailed in the assessment table (refer to Section 8).

Further details on withdrawal of consent or the exercise of participants' data privacy rights are included in the corresponding informed consent form.

9.2.1 Early study termination by the sponsor

The study can be terminated by Novartis at any time for any reason.

Reasons for early termination:

- Unexpected, significant, or unacceptable safety risk to participants enrolled in the study
- Decision based on recommendations from applicable board(s) after review of safety and efficacy data
- Discontinuation of study drug development

In taking the decision to terminate, Novartis will always consider the participant welfare and safety. Should early termination be necessary, participants must be seen as soon as possible and treated as a participant who discontinued from study treatment and treated as a prematurely withdrawn participant. The investigator may be informed of additional procedures to be followed in order to ensure that adequate consideration is given to the protection of the participant's interests. The investigator or sponsor depending on the local regulation will be responsible for informing IRBs/IECs of the early termination of the trial.

9.3 Study completion and post-study treatment

Study completion is defined as when the last participant finishes their 2-month follow up visit and any repeat assessments associated with this visit have been documented and followed-up appropriately by the Investigator (e.g. Each participant will be required to complete the study in its entirety and thereafter no further study treatment will be made available to them in the scope of the trial).

10 Safety monitoring and reporting

10.1 Definition of adverse events and reporting requirements

10.1.1 Adverse events

An adverse event (AE) is any untoward medical occurrence (e.g. any unfavorable and unintended sign [including abnormal laboratory findings], symptom or disease) in a participant or clinical investigation participant after providing written informed consent for participation in the study. Therefore, an AE may or may not be temporally or causally associated with the use of a medicinal (investigational) product.

The investigator has the responsibility for managing the safety of individual participant and identifying adverse events.

Novartis qualified medical personnel will be readily available to advise on study related medical questions or problems.

The occurrence of adverse events must be sought by non-directive questioning of the participant at each visit during the study. Adverse events also may be detected when they are volunteered by the participant during or between visits or through physical examination findings, laboratory test findings, or other assessments.

Adverse events must be recorded under the signs, symptoms, or diagnosis associated with them, accompanied by the following information (as far as possible) (if the event is serious refer to [Section 10.1.2](#)):

1. The severity grade

mild: usually transient in nature and generally not interfering with normal activities

moderate: sufficiently discomforting to interfere with normal activities

severe: prevents normal activities

2. its relationship to fingolimod.

3. its duration (start and end dates) or if the event is ongoing and the outcome of not recovered/not resolved must be reported
4. whether it constitutes a SAE (see [Section 10.1.2](#) for definition of SAE) and which seriousness criteria have been met
5. action taken regarding with study treatment

AEs associated with infections will be recorded on the AE eCRF pages. Refer to [Section 16.7](#) Appendix 7 to see Guidance on monitoring patients with infections.

All adverse events will be treated appropriately per investigators clinical judgement. Treatment may include one or more of the following:

- Dose not changed
- Drug interrupted/permanently discontinued

Refer to [Section 16.7](#) for Guidance on safety monitoring.

6. Conditions that were already present at the time of informed consent should be recorded in medical history of the participant.

Adverse events (including lab abnormalities that constitute AEs) should be described using a diagnosis whenever possible, rather than individual underlying signs and symptoms.

Adverse event monitoring should be continued for at least 30 days following the last dose of study treatment.

Once an adverse event is detected, it must be followed until its resolution or until it is judged to be permanent (e.g. continuing at the end of the study), and assessment must be made at each visit (or more frequently, if necessary) of any changes in severity, the suspected relationship to the interventions required to treat it, and the outcome.

Information about adverse drug reactions for the investigational drug can be found in the Investigator's Brochure (IB).

Abnormal laboratory values or test results constitute adverse events only if they fulfill at least one of the following criteria:

- they induce clinical signs or symptoms
- they are considered clinically significant
- they require therapy

10.1.2 Serious adverse events

An SAE is defined as any adverse event [appearance of (or worsening of any pre-existing)] undesirable sign(s), symptom(s), or medical conditions(s) which meets any one of the following criteria:

- fatal
- life-threatening

Life-threatening in the context of a SAE refers to a reaction in which the participant was at risk of death at the time of the reaction; it does not refer to a reaction that hypothetically might have caused death if it were more severe (please refer to the ICH-E2D Guidelines).

- results in persistent or significant disability/incapacity
- constitutes a congenital anomaly/birth defect
- requires inpatient hospitalization or prolongation of existing hospitalization, unless hospitalization is for:
 - routine treatment or monitoring of the studied indication, not associated with any deterioration in condition (e.g. hospitalization for relapse treatment)
 - elective or pre-planned treatment for a pre-existing condition that is unrelated to the indication under study and has not worsened since signing the informed consent
 - social reasons and respite care in the absence of any deterioration in the participant's general condition
 - treatment on an emergency outpatient basis for an event not fulfilling any of the definitions of a SAE given above and not resulting in hospital admission
- is medically significant, e.g. defined as an event that jeopardizes the participant or may require medical or surgical intervention to prevent one of the outcomes listed above

Medical and scientific judgment should be exercised in deciding whether other situations should be considered serious reactions, such as important medical events that might not be immediately life threatening or result in death or hospitalization but might jeopardize the participant or might require intervention to prevent one of the other outcomes listed above. Such events should be considered as "medically significant". Examples of such events are intensive treatment in an emergency room or at home for allergic bronchospasm, blood dyscrasias, or convulsions that do not result in hospitalization or development of dependency or abuse (please refer to the ICH-E2D Guidelines).

All malignant neoplasms will be assessed as serious under "medically significant" if other seriousness criteria are not met and the malignant neoplasm is not a disease progression of the study indication.

Any suspected transmission via a medicinal product of an infectious agent is also considered a serious adverse reaction.

All reports of intentional misuse and abuse of the product are also considered serious adverse event irrespective if a clinical event has occurred.

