A key pharmacodynamic effect of fingolimod is a dose-dependent reduction of peripheral lymphocyte count to 20 - 30% of baseline values. This is due to the reversible sequestration of lymphocytes in lymphoid tissues. In multiple sclerosis clinical trials, the overall rate of infections (65.1%) at the 0.5 mg dose was similar to placebo [Novartis 2019](#). However, bronchitis, herpes zoster and pneumonia, were more common in Gilenya treated patients [Karlsson G,Francis and Schmouder R,et 2009](#). Serious infections occurred at a rate of 1.6% in the fingolimod 0.5 mg group versus 1.4% in the placebo group [\(2013\) 2.5 Clinical Overview Rationale for changes to Core Data Sheet \(CDS\) / A full review and up date of sections, A full review and update of sections, “Warnings and Precautions”, “Adverse Drug Reactions” and “Interactions”](#) . In a second 2-year placebo controlled study, CFTYD2309, which was reported after approval of fingolimod, the safety profile seen in prior studies was largely confirmed, however in this study herpes zoster was reported more frequently in the fingolimod arms as compared to placebo (2.5% vs. 0.8% respectively) and basal cell carcinomas were more frequent in the fingolimod 0.5 mg group (2.8%) as compared to both, the fingolimod 1.25 mg and the placebo arms (1.6 and 0.6%) respectively. One fatal primary disseminated varicella zoster infection and one fatal herpes simplex encephalitis case have occurred in patients receiving the 1.25 mg/day dose; at the fingolimod 0.5 mg dose, one patient died in the post-marketing setting due to a disseminated varicella zoster infection in the context of high dose steroid treatment.

As part of a post-approval commitment to China's health authorities, Novartis is conducting this post-approval commitment study (PAC) in order to evaluate the efficacy and safety profile of fingolimod in Chinese multiple sclerosis patients. The study will collect safety profile information related to clinical practice setting and long-term follow-up including, but not limited to infections, cardiac and vascular events (e.g. stroke, myocardial infarction, angina pectoris and peripheral vascular disease, second and third degree AV conduction block, hypertension), malignancies, pulmonary events, seizures, MS relapses, atypical severe neurological events and sudden/unexplained death.

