1.2 Purpose

The purpose of this study is to collect 24-month efficacy, safety, tolerability, and health outcome data of fingolimod (0.5 mg per Day) in participants with relapsing multiple sclerosis (RMS) in China. This is a post approval commitment study for fingolimod.

2 Objectives and endpoints

Table 2-1 Objectives and related endpoints

Objective(s)	Endpoint(s)
Primary objective(s)	Endpoint(s) for primary objective(s)

To evaluate the efficacy of fingolimod 0.5mg on annualized relapse rate (ARR) in	
Annualized relapse rate(ARR)

Objective(s)	Endpoint(s)
participants with RMS treated for up to 24 months.	
Secondary objective(s)	Endpoint(s) for secondary objective(s)

To evaluate the safety and tolerability of fingolimod 0.5 mg in participants with RMS treated for up to 24 months.To evaluate the efficacy of fingolimod 0.5 mg on MRI lesions.	
Adverse events (AE) and serious adverse events (SAE)Laboratory tests(hematology, biochemistry)Vital signsElectrocardiogram (ECG)Ophthalmology 
T1 hypo-intense lesion number and volume; T2 lesion volume, new/newly enlarged T2 lesion number; Gd-enhancing T1 lesion number and volume.

3 Study design

This is a 24-month, open-label, multicenter, interventional, single-arm study to collect efficacy, safety and health outcome data of fingolimod (Gilenya) 0.5 mg/day in approximately 100 relapsing multiple sclerosis (RMS) participants in China.

The study will consist of three Phases (see [Figure 3-1](#)):

Screening (up to 1 month): After signing informed consent, participants will enter a Screening Phase to determine eligibility according to inclusion and exclusion criteria.

[figure not shown]
The investigator must ensure that all patients meet the inclusion and exclusion criteria to be eligible to enter the study.

Treatment Period (24 months): On visit Day 1, all eligibility criteria will be confirmed, including a pre-dose ECG and vital signs. The first dose of study drug will be taken in the clinic on Day 1 and the participant will be monitored for at least 6 hours after the first dose administration before discharge. Refer to [Section 16.5](#) for Guidance for monitoring of patients taking their first dose of the study drug.

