8.3 Efficacy

MS relapse activity and neurological impairment of MS as measured by Expanded Disability Status Scale (EDSS) (refer to [Section 16.4](#) for EDSS assessment criteria) will be obtained in order to characterize the disease activity.

8.3.1 Efficacy assessment 1

MS relapse

General definition of relapse: Appearance of a new neurological abnormality or worsening of previously stable or improving pre-existing neurological abnormality, separated by at least 30

days from onset of a preceding clinical demyelinating event. The abnormality must be present for at least 24 hours and occur in the absence of fever (< 37.5 °C) or infection.

Definition of confirmed relapse: A relapse must be confirmed by the Treating Physician. It is recommended that this occur within 7 days of the onset of symptoms. A relapse is confirmed when it is accompanied by an increase of at least half a step (0.5) on the EDSS or an increase of 1 point on two different Functional Systems (FS) of the EDSS or 2 points on one of the FS (excluding Bowel/Bladder or Cerebral FS).

Only confirmed relapses will be included in the primary efficacy analysis. However, the relapse-related analyses will be repeated using all relapses to assess the sensitivity of the results.

Reporting of relapse : A participant may report symptoms indicative of a relapse at a scheduled visit or at any other time. Participants will be instructed to immediately contact the treating physician if he/she develops new or re-occurring or worsening neurological symptoms. At each scheduled visit, the participant will also be asked whether any such symptoms have occurred.

Upon reporting of symptoms indicative of a relapse, the treating physician will assess in an appropriate manner whether the symptoms occur in the presence of fever or infection. If fever or infection can be excluded, a neurological examination by the treating physician must be arranged as soon as possible. If fever or infection cannot be excluded, the neurological examination will be postponed until the fever or the infection has ceased (provided, that the symptoms indicative of a relapse are still present). Treatment with steroids should not begin prior to the assessment by the investigator.

Based on results of the neurological examination (change in FS and EDSS scores), the treating physician will assess if the relapse meets the criteria for “confirmed relapse” as per protocol and record relapse on the Summary of MS Relapses eCRF.

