2.8.1 Adverse events (AEs)

An adverse event (AE) is any untoward medical occurrence (i.e. any unfavorable and unintended sign [including abnormal laboratory findings], symptom or disease) in a clinical investigation subject after providing written informed consent for participation in the study. That means that a subject can report AEs before having started study medication. For reporting purposes, the main focus will be on treatment emergent adverse event (TEAE), defined as any AE which started on or after the day of first dose of study medication or events present prior to the start of treatment but increased in severity based on preferred term.

Except for serious TEAEs and deaths, only TEAEs up to and including the safety cut-off will be included in the analyses. All serious TEAEs and deaths will be included, regardless of the safety cut-off.

TEAEs will be reported by primary system organ class (SOC) and preferred term (PT) according to the most recent Medical Dictionary for Regulatory Activities (MedDRA). The MedDRA version used for reporting the study will be specified in a footnote of the tables, figures or listings (TFLs).

Overview of TEAE will be provided. The number and percentage of subjects reporting any TEAEs (referred to as incidence of any TEAEs in the following) will be summarized by age group, primary SOC and preferred term. Separate summaries will be provided for serious TEAEs, drug related TEAEs, TEAEs leading to permanent discontinuation of study treatment, TEAEs causing study treatment interruption, and most common TEAEs ($\geq 10\%$ in any of the age groups), which could be replaced by listings (for Child or even for both Adult and Child) if more appropriate. Additionally, the incidence of any TEAEs will also be summarized by age group, primary SOC, preferred term, and maximum severity (Mild, Moderate and Severe). Missing severity will not be imputed.

If a subject reported more than one AE within the same primary SOC, the subject will be counted only once with the maximum severity at the SOCs level, where applicable.

All AEs will be presented in listings.

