5.1.4.2 Relapse date imputation

Missing or partial dates are not expected for the start and end dates of relapses on the Summary of MS relapse CRF pages. In case partial dates (unknown day with month and year available) exist in the final database, the following rules will apply:

- The start date will be imputed as the first day of the month or the first dose date if it occurs in the same month as the first dose date.
- The end date will be imputed as the last day of the month or truncated to have a duration of maximally 90 days (whatever comes first).

5.1.4.3 Data handling for relapses within 30 days of onset of previous relapses or relapses with duration beyond 90 days

According to the protocol definition of MS relapses, the start date of a new relapse has to be at least 30 days after the start date of a previous relapse (i.e. start date of a new relapse – start date of a previous relapse ≥ 30). If a relapse is recorded with a start date < 30 days after the start date of a previous relapse, the below data manipulation will be done to combine them into a single relapse by creating a new relapse record with the following information:

- Start date: Take the earliest start date.
- End date: Take the latest end date. If one of the end dates is missing, set it to missing.
- Date of EDSS intended to confirm the relapse:
 - Take the date of EDSS by which the relapse can be confirmed.
 - If more than one EDSS assessments meet the above criterion, take the date of the EDSS from which the worst severity value is derived.
 - If no EDSS assessment meets the above criterion, take the earliest date of EDSS as captured on the Summary of MS Relapse CRF page.
- Severity: Take the value representing the worst case (severe > moderate > mild > missing) (as specified in [Table 5-1](#))
- “Did the relapse affect daily activities?”, “Hospitalization?”, “Steroid used?”, “Recovery status”: For each of these characteristics, take the value representing the worst case (yes > no for the first 3 questions; no > partial > complete recovery for the last question).

Table 5-1 Severity of MS relapses

Mild relapse	Moderate relapse	Severe relapse
EDSS increase of 0.5 point	EDSS increase of 1 or 2 points	Exceeding moderate criteria
or	or	Or
1-point FS change in one to three systems	2-point FS change in one or two systems	Exceeding moderate criteria
	or	Or
	1-point change in four or more systems	Exceeding moderate criteria

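### The SAE definition exempts relapse admissions under a condition that no relapse can meet, so sites may classify them differently and SAE incidence may mix conventions

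*Protocol*

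**What the plan says.** Protocol 10.1.2 lists the criteria that make an adverse event serious. One is that the event "requires inpatient hospitalization or prolongation of existing hospitalization, unless hospitalization is for" one of four listed reasons. The first reason is "routine treatment or monitoring of the studied indication, not associated with any deterioration in condition (e.g. hospitalization for relapse treatment".

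Protocol 8.3.1 defines a relapse as "Appearance of a new neurological abnormality or worsening of previously stable or improving pre-existing neurological abnormality", with conditions on timing, duration and absence of fever or infection. It then sets the confirmation rule: "A relapse is confirmed when it is accompanied by an increase of at least half a step (0.5) on the EDSS", or by specified rises in Functional System scores.

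SAEs are an endpoint for the secondary safety objective (Protocol Table 2-1; SAP Table 1-1). Protocol 1.1 includes relapses in the safety information that the study will collect: "malignancies, pulmonary events, seizures, MS relapses, atypical severe neurological events and sudden/unexplained death". SAP 2.8.1 summarises serious TEAEs by age group, system organ class and preferred term, and adds: "All serious TEAEs and deaths will be included, regardless of the safety cut-off". It has no rule for relapse terms.

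Hospitalisation is recorded for each relapse. SAP 5.1.4.3 uses that item when it merges relapse records less than 30 days apart: "take the value representing the worst case (yes > no for the first 3 questions", hospitalisation being one of those three.

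**The concern.** The exemption joins a condition and an example that point in opposite directions. A site that follows the example reports no relapse admission as an SAE on the hospitalisation criterion. A site that follows the condition reports every one. Both are reasonable readings of the same sentence.

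At stake is the SAE incidence in a post-approval commitment study at around 10 to 15 centres, in a population selected for recent relapses. If sites divide, the pooled percentage counts relapse admissions at some centres and omits them at others, and the planned serious-TEAE table would not show how many were omitted. Because 10.1.3 ties 24-hour reporting to SAE status, the same ambiguity reaches expedited reporting.

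**Working it through.** **Textual check**

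1. *Condition against definition.* The exemption requires no deterioration in condition. A relapse under 8.3.1 is a new abnormality or a worsening of one, and a confirmed relapse also carries a measured rise in EDSS or Functional System score. No relapse so defined is free of deterioration, so the example falls outside the condition it illustrates.
2. *The rest of the list.* Two of the other three exemptions in 10.1.2 (pre-planned treatment of an unrelated condition; social or respite care) also require that the participant has not worsened. Treating absence of worsening as the governing rule fits the pattern of the list.
3. *Other places that might settle it.* Protocol 10.1.1 defines an AE as any untoward medical occurrence and does not exempt relapses. Protocol 8.3.1 directs relapses to their own eCRF page but does not say that they are not AEs. Protocol 10.1.3 requires every SAE to be reported and refers to instructions in the investigator folder, which is not among the documents. SAP 2.8 and 2.8.1 do not mention relapse. Nothing in the visible text decides between the two readings.

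**Illustration of size**

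The documents state no SAE rate, so there is no figure of the plan to reproduce for this endpoint. The plan's negative binomial assumptions can be checked against its own precision statement and then reused.

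Inputs from Protocol 12.8.1 and 6.1.4: ARR 0.25 (assumed range 0.20 to 0.38), k = 1, about 100 participants, 24 months of treatment (taken as 2 years). Assumed, not in the documents: the share h of relapses treated in hospital.

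- *Check of the variance form.* ARR ± 1.96 × √((ARR + k × ARR²)/80) at ARR 0.25 is 0.25 ± 1.96 × √(0.3125/80) = 0.1275 to 0.3725, against the stated 0.13 to 0.37. At ARR 0.38 it is 0.221 to 0.539, against 0.22 to 0.54. The variance form with k = 1 is confirmed.
- *At least one relapse in 24 months.* With mean m = 2 × ARR and k = 1, P = m/(1 + m). This gives 0.40/1.40 = 28.6%, 0.50/1.50 = 33.3% and 0.76/1.76 = 43.2% at ARR 0.20, 0.25 and 0.38.
- *At least one relapse admission.* If each relapse is admitted independently with probability h, P = hm/(1 + hm), and the expected number of admissions in 100 participants is 100 × h × m.

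| ARR | h (assumed) | Relapse admissions per 100 | Participants with at least one |
|---|---|---|---|
| 0.25 | 0.20 | 10 | 0.10/1.10 = 9.1% |
| 0.25 | 0.40 | 20 | 0.20/1.20 = 16.7% |
| 0.25 | 0.60 | 30 | 0.30/1.30 = 23.1% |
| 0.20 | 0.10 | 4 | 0.04/1.04 = 3.8% |
| 0.38 | 0.60 | 45.6 | 0.456/1.456 = 31.3% |

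If every site follows the example, none of these admissions counts on the hospitalisation criterion. If every site follows the condition, all of them count. The last column is the largest shift in SAE incidence for that ARR and h.

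*Mixed practice.* If a quarter of participants are at sites that follow the condition (an assumption), the middle row gives 0.25 × 16.7 = about 4 points.

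**The case against.** The strongest reply is that the text already answers the practical question. Relapse treatment is named as an exempt admission, and no other SAE provision in either document addresses relapse. A reading that reports every relapse admission leaves the example with no effect. A reading that keeps both parts is available: relapse treatment is routine care of the indication, and the condition covers deterioration beyond that. On this view most sites would exempt relapse admissions, and no document shows that sites divide.

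Much of this stands. Exemption is the likelier intention, and divergence between sites is an inference. But the reconciling reading has to be supplied by the reader, because the sentence excludes any deterioration.

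The objection on size also stands. The percentages compare all sites on one reading with all sites on the other. They assume full 24-month follow-up although the plan allows for 20% drop-out, no other SAE in a participant with a relapse admission, and no relapse admission that is serious on another criterion. All three push the figure up.

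A reader might infer that the SAE rate cannot be interpreted, or cannot be compared with earlier fingolimod trials. The documents do not support either. Serious TEAEs are tabulated by preferred term, so relapses that were reported as SAEs can be identified, and the documents give neither the SAE convention nor an overall SAE rate of the earlier trials. Nor do they support an inference that relapse is the commonest foreseeable reason for admission. The mention of relapses in Protocol 1.1 shows that they are collected, not that they are AEs.

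**Conclusion.** The inconsistency is real and lies in the operative SAE definition: the only example of the exemption cannot meet its condition, and no other visible text resolves it. SAE incidence may therefore mix two conventions across sites.

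The reach is limited to the hospitalisation criterion. A relapse can still be serious on other grounds, such as persistent disability or medical significance, and the primary ARR does not depend on SAE status.

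The actual effect on SAE incidence is unknown. The 9 to 23 points at ARR 0.25 are an upper bound for an assumed 20% to 60% of relapses admitted, not an estimate. The wider 4 to 31 points over ARR 0.20 to 0.38 and 10% to 60% admitted carry the same caveat. The possible effect is large enough to justify a cheap clarification.

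**What to change.** 1. **Protocol 10.1.2.** Reconcile the condition and the example so that one rule on hospitalisation for relapse treatment applies at every site. This review does not say which rule. Protocol 14.1 allows changes only by written amendment with the approvals listed there, so a memo to sites is not enough.
2. **SAP 2.8.1.** Tabulate serious TEAEs both including and excluding MS-relapse preferred terms. The difference shows how much of the reported incidence comes from relapse.
3. **Relapse hospitalisations.** Report the number of relapses with hospitalisation from the item on the Summary of MS Relapse page. It is entered by sites, but it does not depend on whether the site called the admission an SAE. The visible SAP uses it only when merging relapse records.

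Items 2 and 3 also serve admissions already classified, which an amendment cannot change retrospectively. The cost is one amended sentence with its approvals and one or two extra tables. No new data are needed.
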